### 8.2.4 Change from Baseline

Change from baseline is calculated as:

- visit value – baseline value.

Percentage change from baseline is calculated as:

- (change from baseline / baseline value) \* 100.

Percent change for geometric mean ACR is calculated as:

- ((geometric mean ACR at a visit / baseline geometric mean ACR) – 1) \* 100%.

If either the baseline or visit value is missing, the change from baseline and percentage change from baseline is missing.

### 8.2.5 Multiple Assessments

All data will be reported according to the nominal visit date for which they were reported (that is, no visit windows will be applied during dataset creation and the visit will not be re-allocated if the actual visit date deviates from the planned date according to the visit schedule in the protocol). In the instance of early discontinuation from the study, data collected at discontinuation from study should be slotted to the closest scheduled visit.

Unscheduled data will not be included in by-visit summaries, but will contribute to values of clinical importance and will appear chronologically in listings. Data from all assessments (scheduled and unscheduled), including multiple assessments, will be included in listings.

If multiple assessments on different days are reported for the same scheduled assessment, then the latest assessment for that scheduled assessment will be analyzed unless as specified otherwise below.

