Subjects receiving CSL346 will be administered an initial loading dose of 3 mg/kg or 6 mg/kg IV, followed by 8 mg/kg or 16 mg/kg SC, respectively, at least 2 hours but no more than 6 hours later. Subsequent SC infusions (8 mg/kg or 16 mg/kg per dose) will be administered every 4 weeks for 12 weeks. Subjects receiving placebo will be administered normal saline using a matched regimen and volume. The primary endpoint (ACR) will be assessed 4 weeks after the last dose of IP.

Study procedures will be conducted as described in the [Schedule of Assessments](#).

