4.3.2 Procedures for Handling Withdrawals

If a subject is withdrawn from the study, attempts will be made to complete and document Follow-up Visits (Visit 10 and EOS). If the subject is unwilling or unable to return for Follow-up Visits, the site should attempt to collect AE information by telephone at 4 and 12 weeks after the last dose of IP.

If the subject is withdrawn from the study after receiving IP, every effort will be made to ensure that the relevant safety assessments are completed. The subject may also be asked by the Investigator to complete other study assessments.

If the subject withdraws from the study and also withdraws consent for disclosure of future information, CSL may retain and continue to use any data collected before such withdrawal of consent.

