7.3 Prohibited Therapies

The following therapies are NOT PERMITTED during the study:

Medication / Therapy	Dose	Prohibited Period of Use	Notes
Mineralocorticoid receptor antagonists, combination treatment with RAS inhibitors and ARB, or direct renin inhibitors ^a	NA	Within 8 weeks before Screening through EOS	NA
Trimethoprim, Cimetidine, Cephalosporins, Probenecid, Aminoglycosides, Ketoconazole, Clofibrate, Dronedarone, and Ranolazine.		Within 4 weeks before Screening through EOS	NA
Fenofibrate or nonsteroidal anti-inflammatory agents not taken as part of a stable regimen ^a		Within 8 weeks before Screening through EOS	NA
Immunosuppressive medications, such as cyclosporine, mycophenolate mofetil, tumor necrosis factor-alpha inhibitors, janus kinase inhibitors, or integrin receptor antagonists		Within 8 weeks before Screening through EOS	Systemic corticosteroids are only permitted at low doses for short-term treatment of acute conditions, such as an allergic reaction or gout
Other investigational agents ^a	N/A	Within 12 weeks before Screening through EOS	This is not applicable if the subject is known to have received a placebo as part of another clinical trial

^a If administration of any prohibited therapy becomes necessary during the study for medical reasons, the subject may be withdrawn from further study treatment and proceed to Follow-up (Section 4.3.2).

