8.1.3 Efficacy Assessments

The efficacy of CSL346 will be assessed based on changes in ACR associated with CSL346 treatment. To minimize intrasubject variability, baseline values for these parameters will be based on the geometric mean values from 3 FMV urine collections on 2 separate occasions (ie, 6 total FMV samples) before the first dose of IP. FMV urine samples for the determination of ACR will be collected as indicated in the [Schedule of Assessments](#). On-treatment assessments of ACR will be the geometric mean values from multiple FMV collections at each time point. Only 2 FMV samples will be collected at Visit 9 because a timed 24-hour sample will also be collected at this Visit. The Follow-up assessment of ACR performed for the primary analysis 4 weeks after the last dose of IP (Visit 10) will be based on the geometric mean of 3 FMV samples. For the EOS Visit, the assessment of ACR will also be based on the geometric mean of 3 FMV samples.

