9.1.3.5 Assessment and Management of Cardiac Adverse Events

A cardiac AESI will be defined as any clinically meaningful change from Baseline in cardiac-related parameters, such as ECG intervals, cardiac troponin levels [Thygesen et al, 2018], or LVEF.

If at any point a subject has signs and symptoms consistent with cardiac ischemia, congestive heart failure, or other unstable cardiac event with or without elevated troponin or BNP levels, the subject should immediately be referred to the emergency department for urgent cardiac evaluation. If a cardiac event cannot be ruled out, the subject should permanently discontinue administration of IP and enter the Follow-up Period of the study. The Investigator, or delegate should notify the Sponsor Medical Monitor of the decision to discontinue IP and complete the AE/SAE/AESI eCRF to provide details related to the event.

Cardiac troponin-I (cTnI) will be measured at the central laboratory during Screening and throughout the subject's participation in the study. Subjects with cTnI above the URL for the assay (defined as exceeding the 99th percentile of a normal reference population) during Screening or Lead-in will be excluded from the study.

In the absence of signs and symptoms of an unstable cardiac event, if any cTnI value reported by the central laboratory during Treatment or Follow-up exceeds the URL, the following guidance will be followed:

- Repeat measurement of cTnI within 48 hours to confirm
- Hold next dose of IP until the following steps are completed
- The subject will be referred to the local cardiologist for cardiac evaluation within 1 week, adhering to local standards of care, as indicated. Every effort should be made to seek evaluation by the same cardiologist used to assess LVEF for Screening. As possible, the same methodology should be used for all study-related cardiac assessments
 - If the local cardiologist finds evidence of myocardial damage or unstable cardiac event, such as new wall motion abnormality (WMA) or decreased LVEF to < 50% on myocardial imaging (Echo, radionuclide imaging, or cardiac magnetic resonance imaging scan), new abnormal delayed enhancement on cardiac magnetic resonance imaging, or new Q-waves or ischemic changes on ECG, contact the Study Medical Monitor to determine if IP can be administered, if additional follow-up is needed, or if IP should be permanently discontinued

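### Visit 10 has no single date after an early stop of IP, and nominal-visit allocation lets an ACR from as early as Day 29 be analysed as Week 16

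*SAP*

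**What the plan says.** **Allocation.** SAP 8.2.5 states that "no visit windows will be applied during dataset creation and the visit will not be re-allocated if the actual visit date deviates". The sentence ends by naming the planned date in the protocol's visit schedule as the reference. One exception follows: "data collected at discontinuation from study should be slotted to the closest scheduled visit".

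**Estimand.** SAP 10.1.1 and 10.1.2 use a treatment-policy strategy, so stopping IP is disregarded. The comparison is at Week 16 (Visit 10), within an MMRM that takes Weeks 2, 4, 8, 12, 16 and 24.

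**Timing of Visit 10 and EOS after an early stop.** The protocol points three ways.
- *By calendar:* the Schedule of Assessments, Table 9 (8.3.2), Table 10 (8.6.1) and 8.6.5 place Visit 10 at Day 113 and EOS at Day 169, each ± 7 days. Section 9.1.3.4 keeps subjects who stop for blood pressure in all study visits.
- *By last dose:* section 3.1 says "The primary endpoint (ACR) will be assessed 4 weeks after the last dose of IP", and 8.1.3 says the same of Visit 10. Section 3.1.4 runs Follow-up for 12 weeks from the last dose. In 9.1.3.5, if a cardiac event cannot be ruled out, "the subject should permanently discontinue administration of IP and enter the Follow-up Period of the study"; Table 13 repeats this. In 7.3, after a prohibited therapy, "the subject may be withdrawn from further study treatment and proceed to Follow-up". Section 4.3.2 asks for Visit 10 and EOS without dating them, and for subjects who cannot return it asks sites to "collect AE information by telephone at 4 and 12 weeks after the last dose of IP".
- *Undated:* 9.1.3.1 to 9.1.3.3 ask only that stoppers continue in Follow-up Visits. SAP 8.4 defines Follow-up only from the IP administration at Visit 9.

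**The concern.** A site whose subject stops after the first dose could reasonably book Visit 10 for Day 29, and nothing in SAP 8.2.5 would move that value out of Week 16. The closest-visit exception speaks of discontinuation from the study. It does not clearly reach a subject who stops IP, stays in the study and attends a visit recorded as Visit 10.

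The primary estimand asks what ACR is at Week 16 whatever happened to treatment. A value taken four weeks after an early last dose answers a different question.

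The supporting analyses would not reliably expose the problem:
- The per-protocol rule for fewer than four doses (SAP 16.7) removes data from last dose + 4 weeks + 1 day, so a value at exactly four weeks stays. Separate exclusions there, for prohibited medication and for a cardiac AESI with heart failure, would catch some cases but not all.
- The tipping-point analysis (SAP 10.1.3) uses the per-protocol set.
- The COVID-19 analysis (SAP 10.1.2) cuts pandemic-related stoppers only beyond 28 days after the last on-schedule infusion.

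**Working it through.** **1. Reproduce the plan's figures** (Protocol 10.1, SAP 4.4). Inputs: SD 0.65, effect ln(1 − 0.27) = −0.315, one-sided alpha 0.10, 94 evaluable subjects (47 per pooled arm).
- SE = 0.65 × √(2/47) = 0.134.
- Power = 85.7% (normal) or 85.4% (t), against 85% stated.
- Critical difference = t(0.90, 92 df) × 0.134 = 0.173, as stated.
- 94/0.94 = 100, as stated. The cap of 124 for 94 completers implies a non-completion ceiling of 1 − 94/124 = 24.2%.

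**2. Where the visits fall on the last-dose reading.** SC doses are due on Days 1, 29, 57 and 85. The last column is the effect left at Day 113 relative to the early Visit 10, *assuming* it follows the approximate 30-day half-life in Protocol 3.3.2.

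| Last SC dose | Visit 10 (+28 d), analysed as Week 16 | EOS (+84 d), analysed as Week 24 | Effect left at Day 113 |
|---|---|---|---|
| 1st (Day 1) | Day 29 | Day 85 | 2^(−84/30) = 0.144 |
| 2nd (Day 29) | Day 57 | Day 113 | 2^(−56/30) = 0.274 |
| 3rd (Day 57) | Day 85 | Day 141 | 2^(−28/30) = 0.524 |

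In the second row, the value actually taken at Week 16 is labelled Week 24, while the Day 57 value stands in for Week 16.

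**3. Size if the effect wanes.** Bias = f × w × 0.315, where f is the share of CSL346 subjects with an early Visit 10 and w is the share of the effect present then but gone by Day 113. The documents give no w. If stopping is equally likely after dose 1, 2 or 3, the mean effect left is (0.144 + 0.274 + 0.524)/3 = 0.314, so w = 0.686. Full effect at the early visit, and attendance by every non-completer, are further assumptions.
- f = 6%: 0.06 × 0.686 × 0.315 = 0.013 ln units; 0.013/0.134 = 0.1 SE.
- f = 24.2%: 0.242 × 0.686 × 0.315 = 0.052 ln units; 0.052/0.134 = 0.4 SE.
- Range over w from 0 to 1: 0 to 0.019 at 6%, and 0 to 0.076 at 24.2%. At w = 1, a labelled 27.0% reduction corresponds to a treatment-policy reduction of 25.6% or 21.2% respectively.

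**4. The opposite case.** Suppose CSL346 stoppers have doubled ACR at the early visit and are back at baseline by Day 113 (assumption). The labelled analysis then understates the effect by f × ln 2 = 0.06 × 0.693 = 0.042, or 0.242 × 0.693 = 0.168.

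**5. No drug effect.** If CSL346 affects neither ACR nor discontinuation, mislabelling is alike in both arms and type I error is not inflated.

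These are simple mean calculations, not an MMRM simulation.

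**The case against.** The strongest reply is that the early Visit 10 is an inference. Every dated table puts Visit 10 at Day 113. For a completer, four weeks after the last dose simply is Week 16. Section 4.3.2 ties only the fallback telephone contact to the last dose, and 9.1.3.4 keeps blood-pressure stoppers in all visits. The SAP sentence itself concerns deviation from the scheduled date. Section 7.3 also refers its cases to 4.3.2, the withdrawal procedure, so the closest-visit exception might cover some of them. All of this stands to the extent that the plan is ambiguous and does not state an early date. It does not remove the problem, because sites can follow either reading and the SAP corrects for neither.

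A reader might go further and infer that the plan systematically overstates the effect in favour of CSL346. The documents do not support that. It needs the full effect to be present at the early visit, but Protocol 3.3.1 rests the expected ACR activity on 12 weeks of dosing. It needs the effect to wane with serum level, but the dose rationale works from a threshold trough of 14.4 µg/mL and predicts that 59% of 16 mg/kg subjects exceed it at Week 24. (That prediction is for a full course at the high dose, so it does not establish persistence after one or two doses either.) It also needs stopping to be unrelated to ACR, but an albuminuria AESI can itself lead to stopping.

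The sizes are also generous. Completers are defined as having received all doses and had the Week 16 ACR, so many non-completers may have no such value. The 24% is a contingency ceiling, not an expected rate.

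**Conclusion.** The point holds as a conflict over visit timing that the SAP's allocation rule leaves uncorrected. On a natural reading of the protocol, an ACR from Day 29, 57 or 85 can enter the primary analysis as Week 16, contrary to the treatment-policy estimand.

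The direction is conditional: overstatement if the effect wanes after stopping, about zero if it persists, reversal if stoppers have a transient ACR rise. The 0.013 and 0.05 ln-unit figures illustrate the waning case only, under generous attendance and equal-timing assumptions. At the planned 6% discontinuation the size is small beside the SE. It deserves correction because it touches the primary endpoint and is cheap to settle before unblinding.

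**What to change.** 1. **Protocol (essential).** Reconcile 3.1, 3.1.4, 4.3.2, 7.3, 8.1.3, Table 10, 9.1.3.4, 9.1.3.5 with Table 13, and SAP 8.4. ACR for Visit 10 and EOS should be collected at Day 113 and Day 169, counted from Day 1, in every randomized subject who remains in follow-up, whether or not IP was stopped. This concerns only when ACR is measured. The rules for stopping IP and for safety follow-up afterwards are for the sponsor to reconcile.
2. **SAP 8.2.5 (safeguard).** For subjects who stop IP early, allocate ACR by actual study day, so that a value outside Day 113 ± 7 is not analysed as Week 16. Say what happens to a value outside every window: Day 141, for instance, is 28 days from both Day 113 and Day 169, so a closest-visit rule would not settle it.

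**Cost.** A clarification of visit timing and one SAP paragraph. There are no extra visits if Visit 10 and EOS simply keep their calendar dates. If the sponsor also keeps attendance four weeks after the last dose, the Day 113 ACR becomes an additional urine collection for those subjects.

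**Downside.** Where Day 113 is not attended, re-allocation generally leaves Week 16 missing, and the MMRM then treats it as missing at random. Re-allocation alone therefore does not restore the estimand; collection at Day 113 does.

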Details related to the collection, preparation, and transfer of blood and urine samples for laboratory assessments will be provided in the laboratory manual. Tests resulting in abnormal central laboratory values during the study period that have been classified by the Investigator as clinically significant should be repeated by the central laboratory as soon as possible after receiving the laboratory report to rule out laboratory error.

Refer to [Section 9.6.2](#) for assessment of other abnormal laboratory values.

Vital Signs

Vital signs include BP (systolic and diastolic), body temperature, and pulse rate. Blood pressure measurements should be taken in triplicate before all other assessments. Vital signs in general will be collected before any blood samples that are collected at the same time point. At Visit 2 (Day -21), BP will be the only vital sign collected.

Subjects must be seated for at least 5 minutes before vital sign measurements are taken. Instructions for measuring BP will be provided in the Manual of Operations. At Visit 4 (Day 1), measurements will be taken predose, 30, 60, and 120 minutes after the first IV dose of IP but before the first SC dose of IP is administered, then 30 and 60 minutes after SC dosing. Additional measurements will be taken at Visit 2, at Visit 5 (Day 8, approximate T_{max}), at Visit 6, before each subsequent SC IP administration (at Visits 7, 8, and 9), and during Follow-up (at Visit 10 and EOS). Analysis will be based on the mean of 3 measurements at each timepoint.

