### **Derivation of ACR**

For the purposes of the analysis of ACR, baseline will be defined as the geometric mean of the 6 values obtained before treatment (3 values from Visit 3 and 3 values immediately before treatment at Visit 4). ACR (mg/g) will be derived from first morning void (FMV) urine samples.

On-treatment assessments of ACR will be the geometric mean values from multiple FMV collections (3 FMV collections, except Visit 9 where only 2 FMV samples will be collected) at each time point.

The ACR will be provided with the lab data. Only the geometric mean values for analysis purpose will be calculated.

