For the purposes of this analysis, baseline will be defined as the geometric mean of the 6 values obtained before treatment (3 values from Visit 3 and 3 values immediately before treatment at Visit 4). For post-treatment, data for ACR will be collected in triplicate. The value to be employed in the analysis of each post-treatment visit will be the geometric mean of the three values. In the event of missing data, the value for a visit will be the average of the values available. There will be only one primary comparison so there is no consideration of adjustment for multiple comparisons. Comparisons of CSL346 dose levels with placebo will be considered exploratory. The primary analysis will be performed using the ITT Analysis Set. That is, the population for which we are estimating the treatment effect is according to the treatment to which subjects were randomized. To facilitate characterization of response, a line graph of ACR will be provided by relative week with the standard error of measurement (SEM) at each time point by treatment, and by treatment and baseline ACR category.

A supplemental analysis will consider the effects of COVID-19 on the primary endpoint. For subjects with treatment discontinuation due to logistical pandemic-related reasons (“Conclusion of Subject Participation” eCRF, reason of “Pandemic Related”), observations

greater than 28 days after last on-schedule SC infusion received will be excluded. For subjects who received no infusions due to logistical pandemic-related reasons, all data will be excluded. For subjects who test positive for COVID-19 infection during the study, observations on or after the diagnosis date will be excluded. If both conditions apply, then data exclusion will begin at (a) 28 days after the last SC infusion or (b) the diagnosis date, whichever is earlier.

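### SAP 8.2.5 lets an early-exit value displace an on-time scheduled value for single-value measures, and leaves the Week 16 ACR undefined when a second FMV set is slotted to it

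*SAP*

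**What the plan says.** SAP 8.2.5 works with nominal visits and applies no visit windows. Three of its rules matter here:

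- For a subject who leaves early, "data collected at discontinuation from study should be slotted to the closest scheduled visit". There is no condition that the visit lacks a value.
- If one scheduled assessment has results from different days, "then the latest assessment for that scheduled assessment will be analyzed unless as specified otherwise below".
- "Unscheduled data will not be included in by-visit summaries", although such data do count towards the clinical-importance flags.

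For ACR a separate rule follows. Under SAP 8.2.7, "On-treatment assessments of ACR will be the geometric mean values from multiple FMV collections". SAP 10.1.2 adds: "The value to be employed in the analysis of each post-treatment visit will be the geometric mean of the three values". Protocol 8.3.2 has those voids collected on consecutive mornings.

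Protocol 4.3.2 directs withdrawn subjects to Visit 10 and EOS. Beyond that, "The subject may also be asked by the Investigator to complete other study assessments". The Schedule of Assessments has no early-termination visit.

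Serum creatinine and eGFR are key secondary in SAP Table 1 and are analysed by MMRM under SAP 10.2. Weight is analysed by a similar model under SAP 10.3.

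**The concern.** Each rule is reasonable alone. Slotting rescues exit data that would otherwise have no visit label, and a latest-value rule settles duplicates. Together they give an off-schedule exit value priority over the value collected when the protocol asked for it. Nothing in 8.2.5 or later in the SAP gives the scheduled value precedence.

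The MMRM takes one value per subject and visit, so a programmer must choose. For single-value measures the text makes that choice, and it selects the wrong record. For ACR the text makes no choice, which leaves the primary endpoint value to programming judgement in those cases.

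Timing adds to this. Protocol 6.3.3 and SAP 4.5.1 lock and unblind the Week 16 data for the interim analysis while some subjects may still be between Week 16 and Week 24. If one of them exits before Day 141, the slotting rule could change a Week 16 value that has already been analysed unblinded.

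**Working it through.** **Planned figure.** Inputs from SAP 4.4: SD 0.65, effect ln(0.73) = −0.315, one-sided alpha 0.10, power 85%, 94 subjects.

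- n per arm = 2 × 0.65² × (1.282 + 1.036)² / 0.315², which rounds up to 46, or 92 in total against the stated 94.
- With 47 per arm, SE = 0.65 × √(2/47) = 0.134. Power is 85.7% by the normal approximation and 85.4% by noncentral t.
- The critical difference by t is −0.173, or −15.9%, as the SAP states.

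The sample size reproduces, and this point does not affect it.

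**Where exits collide with a completed visit.** Protocol Table 9 gives the target days. Midpoints between neighbouring visits decide which is closest:

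| Completed visit | Next visit | Midpoint | Exit days slotted back |
|---|---|---|---|
| Day 15 | Day 29 | 22 | 16–21 |
| Day 29 | Day 57 | 43 | 30–42 |
| Day 57 | Day 85 | 71 | 58–70 |
| Day 85 | Day 113 | 99 | 86–98 |
| Day 113 | Day 169 | 141 | 114–140 |

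For example, a subject attends Visit 10 on Day 113 and leaves on Day 130. The exit is 130 − 113 = 17 days from Week 16 and 169 − 130 = 39 days from EOS, so it is labelled Week 16. It is also the latest value. The largest displacement is 140 − 113 = 27 days. An exit exactly on a midpoint is a tie that the rule does not resolve.

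**What the text then selects.**

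- *Serum creatinine, eGFR, weight:* there is one value per visit and no later rule choosing between days, so the exit value is analysed.
- *ACR:* the voids of one visit always fall on different mornings, so a latest-day rule cannot apply literally without discarding planned voids. The geometric-mean rule governs. With two sets under one visit, SAP 10.1.2 speaks of three values and six are available. SAP Appendix 16.7 sets a minimum number of voids for the Per-Protocol set but does not say which set counts.

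**Size for ACR if the exit set replaced the scheduled set.** Suppose k of 47 CSL346 subjects are affected and each loses a share w of its effect. Then the effect becomes ln(0.73) × (1 − wk/47). Both k and w are assumptions. Power is by the normal approximation, with 85.7% when k = 0:

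| k | w = 0.25 | w = 0.5 | w = 1 |
|---|---|---|---|
| 1 | 85.4% | 85.1% | 84.5% |
| 3 | 84.8% | 83.9% | 82.0% |
| 6 | 83.9% | 82.0% | 77.8% |

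To place w: with the half-life of about 30 days in Protocol 3.3.2, exposure at Day 140 is 0.5^(27/30) = 54% of that at Day 113, and the mean loss over Days 114–140 is 26.5%. If effect followed exposure proportionally, w would lie between about 0.25 and 0.5, and w = 1 is an outer bound. Pooling two equal sets of voids would halve w.

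For serum creatinine, eGFR and weight the documents give no SD or target effect, so no comparable figure can be computed.

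**The case against.** The strongest reply is that a reader might infer that the SAP discards an on-time Week 16 ACR, and it does not say that. The latest-value sentence carries an exception for what is specified below it, and the ACR rule is specified below it. This stands: for ACR the gap is an unresolved choice, not a stated overwrite.

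Second, the triggering data are not planned. A subject who leaves after Visit 10 would be asked for EOS, and FMVs at an exit visit are optional. This also stands and limits the number affected. It does not remove the rule, which the SAP wrote for data collected at exit.

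Third, exit data might be called unscheduled and so kept out of by-visit summaries. That is possible, but it would leave the slotting instruction with little purpose, and the text does not say that a slotted value remains unscheduled.

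Two further inferences fail:

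- A reader might think an exit PK sample becomes a trough. SAP Appendix 16.2 defines the trough as the concentration immediately before the next dose, which such a sample cannot meet.
- A reader might think that repeats of abnormal results, such as those that Protocol 8.1.1 says "should be repeated by the central laboratory as soon as possible after receiving the laboratory report", routinely replace the first result. That requires the repeat to be filed under the scheduled visit, which no section directs.

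**Conclusion.** The point holds in a limited form. For serum creatinine, eGFR and weight, 8.2.5 as written replaces a valid scheduled value with an exit value up to 27 days after the Week 16 target day, and by smaller amounts after earlier visits. For ACR it leaves the visit value undefined when two sets of voids share a label. It also allows interim and final Week 16 values to differ for the same subject.

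The expected effect on the trial is small. With one to three CSL346 subjects affected and w of 0.25 to 0.5, power stays between 85.4% and 83.9% even if the exit set replaces the scheduled set. This rests on assumed counts and on effect tracking exposure. Protocol 3.3.2 predicts that 59% of subjects on 16 mg/kg remain above the target concentration at Week 24, so the loss could be smaller. The documents give no rate of exit between Week 16 and Day 141. The planned 6% drop-out relates to reaching 94 Week 16 completers and cannot be used for it.

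The reason to act is that the rule gives a wrong or programmer-dependent value for each subject affected, and the remedy is nearly free.

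**What to change.** Amend SAP 8.2.5, with a matching line in 8.2.7:

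1. Assign early-exit data to the closest visit at which that assessment is scheduled, and only if the subject has no scheduled value there. Otherwise list them only.
2. Where a valid scheduled collection exists, it takes precedence over later off-schedule or repeat values. Use a repeat in its place only if the scheduled sample was technically invalid. Otherwise repeats count only towards the clinical-importance flags.
3. For ACR, compute the visit value only from the FMVs of the scheduled collection.

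The cost is a few sentences and a small change to dataset derivation. The downside is that a few off-schedule exit values are listed instead of analysed.
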